9. ADVERSE EVENTS/SERIOUS ADVERSE EVENTS

9.1. ADVERSE EVENTS - DEFINITION

An adverse event (AE) is any undesirable event that occurs to a subject during a study, whether or not that event is considered study drug-related. Monitoring for AEs will start at dosing. Examples include:

- Any treatment-emergent signs and symptoms (events that are marked by a change from the subject's baseline/entry status [e.g., an increase in severity or frequency of pre-existing abnormality or disorder])
- All reactions from study drug, an overdose, abuse of drug, withdrawal phenomena, sensitivity or toxicity to study drug
- Apparently unrelated illnesses
- Injury or accidents (Note: if a medical condition is known to have caused the injury or accident, the medical condition and the accident should be reported as two separate medical events [e.g., for a fall secondary to dizziness, both "dizziness" and "fall" should be recorded separately])
- Extensions or exacerbations of symptoms, subjective subject-reported events, new clinically significant abnormalities in clinical laboratory, physiological testing or physical examination

All AEs, whether or not related to the study drug, must be fully and completely documented on the AE page of the CRF and in the subject's clinical chart.

In the event that a subject is withdrawn from the study because of an AE, it must be recorded on the CRF as such. The subject should be followed and treated by the Investigator until the abnormal parameter or symptom has resolved or stabilized.

The Investigator must report all directly observed AEs and all spontaneously reported AEs. The Investigator will ask the subject a non-specific question (e.g., "Have you noticed anything different since your dose of the study medication?") to assess whether any AEs have been experienced since the last assessment. AEs will be identified and documented on the AE CRF in appropriate medical terminology. The severity and the relationship to the study drug will be determined and reported on the CRF (see below).

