^a Mean exposure for male and female rats combined on last day of study

^b Mean exposure for patients after 100 mg b.i.d. dose of PTI-125 on Day 28 (CSR PTI-125-03)

A 28-day repeat dose oral toxicity study in dogs that included a 28-day drug-free recovery period used PTI-125 dose levels up to and including 200 mg/kg/day (equivalent to 4,000 mg/m²). Findings included slight muscle fasciculations in some animals at the high dose only, an increase in blood pressure in high dose females, and sporadic alterations in clinical chemistry profiles at the high dose. All observations resolved during the recovery period. A NOEL could not be determined, and the NOAEL was determined to be 100 mg/kg/day (equivalent to 2,000 mg/m²). Safety margins based on this study are shown in **Table 2**.

Table 2. Safety Margin for a 100 mg b.i.d. Human Dose Based on the 4-week Dog Tox

| NOAEL (mg/kg) | C _{max} (ng/mL) | | AUClast (h) | r*ng/mL) | Dog-to-Human Ratio (Safety Margin) | | |
|------------------|--------------------------------|-------|------------------|--------------------|---------------------------------------|---------------------|--|
| | mg/kg) Dog ^a Hui | | Dog ^a | Human ^b | C _{max} | AUC ₀₋₂₄ | |
| 100 | 49,000 | 1,104 | 214,000 | 8,483 | 44.4 | 25.2 | |

^a Mean exposure for male and female dogs combined on last day of study

^b Mean exposure for patients after 100 mg b.i.d. dose of PTI-125 on Day 28 (CSR PTI-125-03)

A subsequent 13-week repeat dose oral toxicity study with a 28-day recovery in dogs used doses of 25, 75 and 150 mg/kg/day. The toxicological response was characterized primarily by increased incidence of emesis and salivation (sometimes extreme), and decreased food consumption in 150 mg/kg animals (reversible). There were occasional incidences of muscle fasciculations, and a few isolated incidences of tremors, lying down, reluctance to stand, and hypoactivity (generally slight). Based the severity and time course of these observations, the NOAEL was established at 150 mg/kg/day. The Day 90 C_{max} at this dose was 70.3 and 71.8 µg/mL in males and females, respectively, and the Day 90 AUC_{last} was 456 and 439 h•µg/mL in males and females, respectively. Safety

margins based on this study are shown in Table 3.

| NOAEL (mg/kg) | C _{max} (ng/mL) | | AUClast (h) | r*ng/mL) | Dog-to-Human Ratio (Safety Margin) | | |

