4. SUMMARY OF STUDY DESIGN

This is a Phase 2b, multi-center, randomized, double-blind, placebo-controlled, study of PTI-125 in mild-to-moderate AD patients, 50-85 years of age. Approximately sixty (60) patients will be enrolled into the study and randomized to one of three cohorts. Cohorts will receive placebo or PTI-125 at 50 or 100 mg b.i.d. (n=20 per group). Placebo or PTI-125 will be administered as coated tablets.

There will be two screening visits within 30 days of start of the study. Patients meeting initial screening criteria, including a Mini-Mental State Examination (MMSE) score ≥ 16 and ≤ 26 will return for a CSF draw at a second screening visit to confirm that the A β /tau Index is indicative of AD (final inclusion criterion). This CSF sample will also serve as baseline measurement for the YKL40 neuroinflammation and other potential CSF biomarker assays. Cambridge Cognition testing will be conducted at the second screening visit, Day 1, and at the end of the study. Patients will be assessed for suicidality via the Columbia Suicide Severity Scale (C-SSRS) during the first and last visits.

Patients will report to clinic the morning of Day 1. The following will be conducted prior to dosing: Cambridge Cognition testing, a full physical exam, an ECG and a blood draw for clinical labs and biomarkers (PTI-125Dx and mTOR). After dosing, patients will be monitored for adverse events and vital signs will be taken through 4 h. Patients will return to the clinic on Days 7, 14 and 28.

PK blood samples will be obtained prior to the first dose on Day 14 for C_{min} values. On Day 28, there will be a CSF draw after the last dose, and an additional PK blood sample will be obtained after this CSF draw for calculation of CSF/plasma ratio.

Blood draws for clinical laboratory testing will be performed at screening and on Days 1, 7, 14 and 28. Safety assessments of vital signs and listening to heart and lungs will be conducted at all visits. ECGs will be conducted on Days 7, 14 and 28.

Blood samples for testing in PTI-125Dx, the companion diagnostic/biomarker, mTOR activation and other potential blood-based biomarkers will be drawn on Day 1 and Day 28. The Day 28 blood sample will also be used for APOE genotyping. A CSF sample collection will be performed on Day 28 for neurogranin, neurofilament light chain, total tau, pTau (T181), A β_{42} , A β_{40} , YKL40, IL-6, IL-1 β , TNF α and other potential CSF biomarker assays as well as bioanalysis of PTI-125.

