5.2. INCLUSION CRITERIA

Each patient must comply with the following Inclusion Criteria:

- 1. Ages \geq 50 and \leq 85 years
- 2. Informed consent form (ICF) signed by the subject or legally acceptable representative. If a legally acceptable representative signs the ICF, a notation of capacity of the subject must be noted.

- 3. Clinical diagnosis of dementia due to possible or probable AD consistent with criteria established by a workgroup of the National Institute on Aging and the Alzheimer's Disease Association.
- 4. MMSE score ≥ 16 and ≤ 26 at screening, OR if ≥ 26 , a prior CSF total tau/A β_{42} ratio ≥ 0.28 . (A new CSF draw would be required for analysis of pre-dose biomarkers.)
- 5. If female, postmenopausal for at least 1 year
- 6. Patient living at home, senior residential setting, or an institutional setting without the need for continuous (i.e. 24-h) nursing care
- 7. General health status acceptable for participation in the study
- 8. Fluency (oral and written) in English or Spanish
- 9. If receiving memantine, rivastigmine, galantamine or an AChEI, receiving a stable dose for at least 3 months (90 days) before screening and with continuous dosing for at least 3 months. If receiving donepezil, receiving any dose lower than 23 mg once daily. Multiple medications are allowed.
- 10. The patient is a non-smoker for at least 3 years.
- 11. The patient or legal representative must agree to comply with the drawing of blood samples for the PK assessments, laboratory assessments and PTI-125Dx, and with a lumbar puncture and the drawing of CSF samples for biomarker assessments.
- 12. The patient has a ratio of total tau/A β_{42} in CSF that indicates AD. This value (total tau/A β_{42}) will be ≥ 0.28 .
- 13. Patient has a caregiver or legal representative responsible for administering the drug and recording the time.

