7.2.7. End-of-study Follow-up

Patient will receive a follow-up phone call 7-14 days after the last dose. If needed, a follow-up clinic visit will be scheduled.

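### The only active adverse-event enquiry is put to the patient, who has dementia; the caregiver or legal representative whom every patient must have should be asked as well

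*Protocol*

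**What the plan says.** **Enquiry.** Protocol Section 9.1 describes one active enquiry: "The Investigator will ask the subject a non-specific question", the purpose being "to assess whether any AEs have been experienced since the last assessment". The same section adds two passive routes: "The Investigator must report all directly observed AEs and all spontaneously reported AEs". It does not say who may make a spontaneous report.

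**Population.** Inclusion criterion 3 in Section 5.2 requires "Clinical diagnosis of dementia due to possible or probable AD". Section 4 describes initial screening as "including a Mini-Mental State Examination (MMSE) score ≥ 16 and ≤ 26"; criterion 4 also admits higher scores with a qualifying earlier CSF ratio. Criterion 2 allows a representative to sign consent.

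**Caregiver.** Criterion 13 reads "Patient has a caregiver or legal representative responsible for administering the drug and recording the time". The opening of Section 7 has the caregiver sign the consent form, and Section 7.2.3 has the caregiver give the drug at home. No section asks the caregiver about AEs, requires the caregiver to attend visits, or provides a caregiver AE diary.

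**Other places that look to the patient.** Section 7.2.7 says "Patient will receive a follow-up phone call 7-14 days after the last dose". The severity and causality ratings in Sections 9.2 and 9.3 name the subject's report and the physician's own observations or experience among their inputs, but not the caregiver. In Section 9.5 it is the subject who is told to contact the study physician after a serious event. Sections 7.2.3 to 7.2.6 list AE monitoring without saying how it is done.

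**Analysis.** SAP Section 7.0 summarises safety descriptively by treatment level, with no tests between levels.

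**The concern.** The person asked to recall the interval is the one whose memory is impaired. The person who gives the drug twice a day, and is best placed to notice a change at home, is not asked. A site that follows Section 9.1 to the letter will hear from the caregiver only if the caregiver happens to speak up, and that is likely to vary between sites.

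Safety is among the first-named objectives in Protocol Section 3 and SAP Section 1.1. With 20 patients per arm and a purely descriptive analysis, what is said about symptomatic AEs rests on which events reach the eCRF. One missed case is a large part of the evidence on an uncommon event.

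The animal work shows the kind of sign at issue. In the 13-week dog study, "There were occasional incidences of muscle fasciculations, and a few isolated incidences of tremors", along with hypoactivity and lower food intake. An observer at home can see such signs, whereas a patient with dementia may not remember or mention them.

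**Working it through.** The documents state no AE rate, capture rate or safety power, so there is no figure of the plan's to reproduce. Two things can be checked: the recall interval, and how sensitive an arm of 20 is to incomplete capture.

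**1. Recall intervals**

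Inputs: visits on Days 1, 7, 14 and 28 (Protocol Section 4); follow-up visits may move by 2 days either way (Section 7.2); call 7 to 14 days after the last dose (Section 7.2.7).

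Day 1 is not a follow-up visit, so only the far end of the first interval can move (+2). Both ends of the later intervals can move (+4).

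| Interval | Nominal | Longest with windows |
|---|---|---|
| Day 1 to Day 7 | 7 − 1 = 6 days | 6 + 2 = 8 days |
| Day 7 to Day 14 | 14 − 7 = 7 days | 7 + 4 = 11 days |
| Day 14 to Day 28 | 28 − 14 = 14 days | 14 + 4 = 18 days |
| Last dose to call | 7 to 14 days | as stated |

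**2. Chance that an arm records no case (illustration)**

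Inputs: n = 20 per arm (Protocol Section 4). The true risk p and the capture share s (the probability that an affected patient's event is recorded by any route) are assumptions; neither is in the documents. Patients are treated as independent.

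Formula: P(no case recorded) = (1 − p × s)^20. Expected number of patients with a recorded event = 20 × p × s.

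For p = 10%:

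| Capture share s | 1 − p × s | P(no case recorded) | Expected recorded |
|---|---|---|---|
| 100% | 0.900 | 0.900^20 = 12% | 2.0 |
| 75% | 0.925 | 0.925^20 = 21% | 1.5 |
| 50% | 0.950 | 0.950^20 = 36% | 1.0 |
| 25% | 0.975 | 0.975^20 = 60% | 0.5 |

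For other assumed risks, over the same four shares in the same order, P(no case recorded) is:

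- p = 5%: 36%, 47%, 60%, 78%
- p = 20%: 1%, 4%, 12%, 36%

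Because s covers every route, a caregiver who volunteers events already raises it. The tables show what is at stake if s is low; they do not show that it is.

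**The case against.** The strongest reply is that Section 9.1 governs one route among several. Spontaneous reports must be recorded whoever makes them, and a caregiver who signs the consent form and gives every home dose is well placed to make them. Section 9.1 also counts new clinically significant laboratory, physiological and examination findings as AEs. Laboratory tests and vital signs recur on Days 7, 14 and 28, and Appendix A has ECGs on Days 14 and 28. None of these depends on recall. Sites may well ask caregivers anyway. All of this stands, and it limits the point to symptomatic events between visits that nobody volunteers and no test picks up.

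A reader might also infer stronger things that the documents do not support:

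- *That events will be under-reported, by a known amount.* No capture rate is given. Under-recording is a reasonable inference, not a demonstrated fact.
- *That reporting will differ by arm because the drug is expected to improve memory.* This needs a memory effect within 28 days large enough to change AE reporting. Under the blind, the more natural expectation is a loss in all arms.
- *That the liver stopping rule is undermined.* Of the four criteria in Section 7.1, three are purely biochemical. The symptom-based one matters only once ALT or AST is at least 2 × ULN.
- *That the animal findings are expected risks in patients.* The protocol does not say so. The 13-week dog study's NOAEL carries stated margins of 64.3 (Cmax) and 52.7 (AUC) in Table 3. The slight convulsions in a 7-day dog study occurred in one of six animals at 300 mg/kg/day and in none at 1000 mg/kg. These findings illustrate what an observer could notice, nothing more.

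A practical objection is that no rule makes the caregiver attend visits, and that criterion 13 can be met by a legal representative instead. That is fair, and the fix allows for both.

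**Conclusion.** The point holds as a gap in how AEs are sought. Followed as written, the plan puts its only active question to a patient with dementia over nominal intervals of up to 14 days (18 with windows), and makes its post-treatment call to the same person, while a second informant required at entry is not used. This is a stated method that will tend to capture less, not merely an omitted detail.

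The likely effect is under-recording of symptomatic, between-visit events, mainly as lower absolute AE rates in all arms and a greater chance that an uncommon event goes unseen in 20 patients. The rise from 12% to between 21% and 60% in the chance of recording no case rests on an assumed 10% risk and assumed capture of 75% down to 25%. The actual size cannot be estimated from the documents. The change is worth making because it is cheap and uses someone the protocol already requires.

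**What to change.** **Section 9.1.** Replace the sentence on the non-specific question with: *At every visit and at the follow-up call the investigator will ask the non-specific question of the patient and of the caregiver or legal representative (in person, or by phone if not present), and will record who reported each AE.*

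**Section 7.2.7.** State that the follow-up call includes the caregiver or legal representative as well as the patient.

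**Cost.** Two wording changes, one eCRF field for the source of the report, and an occasional short phone contact when the caregiver or representative is not at the visit. No visit is added. AE counts may be slightly higher, which should be expected when they are set beside studies that asked only the patient.

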9.2. Adverse Events - Severity Rating

The severity of each AE should be characterized and then classified into one of three clearly defined categories as follows:

- Mild the AE does not interfere in a significant manner with the subject's normal functioning level. It may be an annoyance.
- Moderate the AE produces some impairment of functioning but is not hazardous to health. It is uncomfortable or an embarrassment.
- Severe the AE produces significant impairment of functioning or incapacitation and is a definite hazard to the subject's health.

These three categories are based on the Investigator's clinical judgment, which in turn depends on consideration of various factors such as the subject's report, and the physician's observations. The severity of the AE should be recorded in the appropriate section of the Adverse Event CRF.

9.3. Adverse Events - Relationship to Study Drug

The relationship of each AE to the study drug will be classified into one of three defined categories as follows:

- Unlikely a causal relationship between the AE and the study drug is unlikely.
- Possible a causal relationship between the AE and the study drug is possible.
- Probable a causal relationship between the AE and the study drug is probable. For example, the AE is a common adverse event known to occur with the pharmacological class the study drug belongs to; or the AE abated on study drug discontinuation and reappeared upon rechallenge with the study drug.

These three categories are based on the Investigator's clinical judgment, which in turn depends on consideration of various factors such as the subject's report, the timing of the AE in relationship to study drug administration/discontinuation, the physician's observations and the physician's prior experience. The relationship of the AE to the study drug will be recorded in the appropriate section of the Adverse Event eCRF.

9.4. SERIOUS ADVERSE EVENTS AND UNEXPECTED ADVERSE EVENTS - DEFINITIONS

A Serious Adverse Event (SAE) includes (but is not limited to) an experience occurring at any dose that results in any of the following outcomes:

- Death
- A life-threatening event (i.e., the subject is at immediate risk of death from the reaction as it occurs). "Life-threatening" does not include an event that, had it

occurred in a more serious form, might have caused death. For example, druginduced hepatitis that resolved without evidence of hepatic failure would not be considered life-threatening even though drug-induced hepatitis can be fatal.

- In-patient hospitalization (hospital admission, not an emergency room visit) or prolongation of existing hospitalization.
- A persistent or significant disability/incapacity (i.e., a substantial disruption of the subject's ability to carry out normal life functions).
- A congenital anomaly/birth defect.

In addition, medical and scientific judgment should be exercised in deciding whether other situations should be considered an SAE (i.e., important medical events that may not be immediately life-threatening or result in death but may jeopardize the subject or may require medical or surgical intervention to prevent one of the other outcomes listed in the definition above). Examples of such medical events include (but are not limited to): allergic bronchospasm requiring intensive treatment in an emergency room or at home, blood dyscrasias or convulsions that do not result in in-patient hospitalization, or the development of drug dependency or drug abuse.

An **unexpected** AE is one for which the specificity or severity is not consistent with the current Investigator's Brochure. For example, hepatic necrosis would be unexpected (by virtue of greater severity) if the Investigator's Brochure only listed elevated hepatic enzymes or hepatitis.

Similarly, cerebral thromboembolism and cerebral vasculitis would be unexpected (by virtue of greater specificity) if the Investigator's Brochure only listed cerebral vascular accidents.

9.5. SERIOUS ADVERSE EVENTS REPORTING

The reporting of SAEs by the Sponsor to Regulatory Authorities (e.g., FDA) is a regulatory requirement. Each Regulatory Agency has established a timetable for reporting SAEs based upon established criteria. Likewise, it is the responsibility of the Principal Investigator to report SAEs to their EC/IRB.

All SAEs must be reported immediately (within 24 h of learning of the event) by telephone to:

[name], MD Cassava Sciences, Inc. Email: [contact] [contact] Do not delay reporting a suspected SAE to obtain additional information. Any additional information, if collected, can be reported to the Sponsor as a follow-up to the initial report.

A completed SAE report form must be faxed within five working days to the medical monitor. SAEs must also be reported to the responsible EC/IRB immediately.

In the case of a death or other SAE that has occurred within 30 days after receiving study drug, the Principal Investigator must also report such an event within 24 hours of being notified. Your local EC/IRB may also require these reports.

In the event of any SAE (other than death), the subject will be instructed to contact the study physician (Principal Investigator or designee) using the phone number provided in the Informed Consent Form. All patients experiencing an SAE will be seen by a Principal Investigator or designee as soon as feasible following the report of an SAE.

10. STATISTICAL CONSIDERATIONS

10.1. RANDOMIZATION

Randomized treatments will be assigned by patient numbers in a randomly generated numeric sequence.

The randomization code will not be revealed to study patients, investigators, clinical staff or study monitors until all patients have completed therapy and the database has been finalized and locked.

Under normal circumstances, the blind should not be broken. The blind may be broken only if specific emergency treatment is indicated. The date, time and reason for the unblinding must be documented on the case report form, and the medical monitor must be informed as soon as possible.

10.2. ANALYSIS POPULATIONS

All patients who receive study medication will be included in analyses for safety, biomarkers and cognition.

10.3. PHARMACOKINETIC PARAMETERS

The only plasma PK parameters to be collected from this study are the C_{min} values from blood samples taken prior to dosing on Days 7 and 14 and the sample on Day 28

collected just after the CSF draw.

A CSF to plasma ratio will be determined using the Day 28 CSF and plasma samples.

